1. ABBREVIATIONS

Abbreviation	Explanation
AE	Adverse Event
ALT	Alanine aminotransferase
ANCOVA	Analysis of covariance
AST	Aspartate aminotransferase
ATC	Anatomic therapeutic class
CI	Confidence interval
CMH	Cochran-Mantel-Haenszel
CRF	Case Report Form
CRN	Clinical Research Network
CRO	Clinical Research Organization
CSR	Clinical Study Report
CTCAE	Common Terminology Criteria for Adverse Events
ECG	Electrocardiogram
eCRF	Electronic case report form
ELF	Enhanced liver fibrosis test
FAST	FibroScan-AST score
FGF-21	Fibroblast Growth Factor 21
FIB-4	Fibrosis-4 index
GGT	Gamma-glutamyl transferase
HbA1c	Glycated hemoglobin
ICH	International Council for Harmonization
IDMC	Independent Data Monitoring Committee
INR	International normalized ratio
ITT	Intent-to-treat population
IWRS	Interactive Web Response System
kg	Kilogram
LDL-C	Low-density lipoprotein cholesterol
LLN	Lower limit of normal
max	Maximum
MedDRA	Medical Dictionary for Regulatory Activities
min	Minimum
mITT	Modified intent-to-treat population
mmHg	Millimeters of mercury
MMRM	Mixed model for repeated measures
MRI-PDFF	Magnetic Resonance Imaging-Proton Density Fat Fraction
ms	Millisecond
N or n	Number of subjects
NAFLD	Nonalcoholic fatty liver disease
NAS	NAFLD activity score
NASH	Nonalcoholic steatohepatitis

Abbreviation	Explanation
NCI	National Cancer Institute
PD	Pharmacodynamic
PK	Pharmacokinetic
PO	Orally
PRO-C3	N-Terminal Type III Collagen Propeptide
PT	Preferred term
Q1	First Quartile
Q3	Third Quartile
QD	Once daily
SAE	Serious adverse event
SAF	Safety Analysis Population
SAP	Statistical analysis plan
SD	Standard Deviation
SI	International System of Units
SNPs	Single-Nucleotide Polymorphisms
SOC	System organ class
T2DM	Type 2 Diabetes Mellitus
TEAE	Treatment-Emergent Adverse Event
TIMP-1	Tissue Inhibitor of Metalloproteinase-1
ULN	Upper limit of normal

2. INTRODUCTION

The statistical analysis plan (SAP) corresponds to the study number SB2640-CLIN-007: “A Phase 2b, Multi-Center, Double-Blind, Randomized, Placebo Controlled Study of the Safety and Efficacy of TVB-2640 in Subjects with Nonalcoholic Steatohepatitis (FASCINATE-2)”. The SAP comprises the protocol pre-planned interim and final analyses and will be the basis for the analyses in support of the Clinical Study Report (CSR). The SAP was based on the study protocol version 4.0 dated 06 September 2023 and CRF dated 24 February 2023. The final sponsor-approved version of the SAP must occur prior to unblinding of the study database and the final analyses.

3. STUDY OBJECTIVES

3.1. Co-primary Objectives

- To evaluate the effect of TVB-2640 50 mg PO QD compared with matching placebo in noncirrhotic subjects with nonalcoholic steatohepatitis (NASH) and F2-F3 fibrosis
 - Histological improvement at Week 52 in nonalcoholic fatty liver disease (NAFLD) activity score (NAS) (i.e., ≥ 2 points improvement in NAS with ≥ 1 point improvement in ballooning or inflammation) and without worsening of fibrosis (by NASH Clinical Research Network [CRN] fibrosis score)
 - Resolution of steatohepatitis and no worsening of liver fibrosis (by NASH CRN fibrosis score). Resolution of steatohepatitis is defined as absence of fatty liver disease or isolated or simple steatosis without steatohepatitis and a NAS of 0 or 1 for inflammation, 0 for ballooning, and any value for steatosis

AND

Histological improvement in NAS (≥ 2 points improvement in NAS) at Week 52

- To evaluate the safety and tolerability of TVB-2640 50 mg PO QD in subjects with confirmed NASH and liver fibrosis.

3.2. Secondary Objectives

- To evaluate the effect of TVB-2640 50 mg QD compared with matching placebo on the proportion of subjects with $\geq 8\%$ liver fat content at Baseline who achieve a $\geq 30\%$ relative reduction in liver fat content as assessed by magnetic resonance imaging-proton density fat fraction (MRI-PDFF) at Week 26.
- To evaluate the effect of TVB-2640 50 mg QD compared with matching placebo on the proportion of subjects with $\geq 8\%$ liver fat content at Baseline who achieve a $\geq 30\%$ relative reduction in liver fat content as assessed by MRI-PDFF at Week 52.
- To evaluate the effect of TVB-2640 50 mg QD compared with matching placebo on fibrosis as assessed by ≥ 1 stage of fibrosis improvement by NASH CRN score) without worsening of steatohepatitis (no increase in NAS for ballooning, inflammation, or steatosis) at Week 52.

- To evaluate the effect of TVB-2640 50 mg QD compared with matching placebo on fibrosis as assessed by ≥ 1 stage of fibrosis improvement by NASH CRN score without increasing of total NAS scores at Week 52.
- To evaluate the effect of TVB-2640 50 mg QD compared with matching placebo on fibrosis as assessed by ≥ 1 stage of fibrosis improvement by NASH CRN score without any worsening of NASH (no worsening of ballooning and lobular inflammation, a 1 grade change in steatosis may be acceptable) at Week 52.
- To evaluate the effect of TVB-2640 50 mg QD compared with matching placebo on the proportion of subjects experiencing **both** of the following at Week 52:
 - Resolution of steatohepatitis on overall histopathological reading and no worsening of liver fibrosis on NASH CRN fibrosis score. Resolution of steatohepatitis is defined as absent fatty liver disease or isolated or simple steatosis without steatohepatitis and a NAS score of 0–1 for inflammation, 0 for ballooning, and any value for steatosis.

AND

- Improvement in liver fibrosis greater than or equal to one stage (NASH CRN fibrosis score) and no worsening of steatohepatitis (defined as no increase in NAS for ballooning, inflammation, or steatosis).
- To evaluate the effect of TVB-2640 50 mg QD compared with matching placebo on the proportion of subjects experiencing **both** of the following at Week 52:
 - Histological improvement at Week 52 in NAS (i.e., ≥ 2 points improvement in NAS with ≥ 1 point improvement in ballooning or inflammation) and without worsening of fibrosis (by NASH CRN fibrosis score)

AND

- Improvement in liver fibrosis greater than or equal to one stage (NASH CRN fibrosis score) and no worsening of steatohepatitis (defined as no increase in NAS for ballooning, inflammation, or steatosis).
- To evaluate the effect of TVB-2640 50 mg QD compared with matching placebo on resolution of steatohepatitis and no worsening of liver fibrosis (by NASH CRN fibrosis score). Resolution of steatohepatitis is defined as absence of fatty liver disease or isolated or simple steatosis without steatohepatitis and a NAS of 0 or 1 for inflammation, 0 for ballooning, and any value for steatosis at Week 52.
- To evaluate the effect of TVB-2640 50 mg QD compared with matching placebo on histological improvement (decrease) at Week 52 in NAS by ≥ 1 point.
- To evaluate the effect of TVB-2640 50 mg QD compared with matching placebo on histological improvement (decrease) at Week 52 in NAS by ≥ 2 points.
- To evaluate the effect of TVB-2640 50 mg QD compared with matching placebo on liver fat content as assessed by MRI-PDFF at Week 26.
- To evaluate the effect of TVB-2640 50 mg QD compared with matching placebo on liver fat content as assessed by MRI-PDFF at Week 52.

- To evaluate the effect of TVB-2640 50 mg QD compared with matching placebo on NASH resolution (defined as absence of fatty liver disease or isolated or simple steatosis without steatohepatitis and a NAS of 0 or 1 for inflammation, 0 for ballooning, and any value for steatosis) at Week 52.
- To determine the effect of TVB-2640 50 mg QD compared with matching placebo on change from Baseline at 26 and 52 weeks in alanine aminotransferase (ALT), aspartate aminotransferase (AST), and gamma-glutamyl transferase (GGT).
- To determine the effect of TVB-2640 50 mg QD compared with matching placebo on the change from Baseline at 26 and 52 weeks in low-density lipoprotein cholesterol (LDLC) and other lipid levels.
- To determine the effect of TVB-2640 50 mg QD compared with matching placebo on the change from Baseline at 52 weeks in the amount of collagen/fibrous area and fibrosis score, assessed by digital pathology.
- To determine the effect of TVB-2640 50 mg QD compared with matching placebo on the change from Baseline at 26 and 52 weeks in fasting insulin, fasting glucose, homeostatic model assessment of insulin resistance (HOMA-IR), adipose tissue insulin resistance (adipo-IR), and glycosylated hemoglobin (HbA1c) levels.
- To determine the effect of TVB-2640 50 mg QD compared with matching placebo on the change from Baseline at 26 and 52 weeks in fibroblast growth factor 21 (FGF-21), adiponectin, and other NASH biomarker levels.
- To determine the effect of TVB-2640 50 mg QD compared with matching placebo on change from Baseline at 26 and 52 weeks in FibroScan® and controlled attenuation parameter (CAP) score.
- To determine the effect of TVB-2640 50 mg QD compared with matching placebo on N-terminal type III collagen propeptide (PRO-C3) levels and other fibrosis biomarkers on change from Baseline at Weeks 4, 13, 26, and 52.
- To determine the effect of TVB-2640 50 mg QD compared with matching placebo on change from Baseline at 26 and 52 weeks on enhanced liver function (ELF) score.

3.3. Exploratory Objectives

- To evaluate the effect of TVB-2640 50 mg QD compared with matching placebo on the proportion of subjects with $\geq 8\%$ liver fat content at Baseline who achieve a $\geq 30\%$ relative reduction in liver fat content as assessed by MRI PDFF AND achieve ≥ 17 U/L reduction in ALT at Week 52.
- To determine the effect of TVB-2640 50 mg QD compared with matching placebo on FibroScan-AST (FAST) score at Weeks 26 and 52.
- To determine the effect of TVB-2640 50 mg QD compared with matching placebo on

select fibrosis biomarkers (including at least tissue inhibitor of metalloproteinase-1 [TIMP1]) at Weeks 4, 13, 26, and 52.

[figure not shown]
- To determine the effect of TVB-2640 50 mg QD compared with matching placebo on lipidomic biomarkers (including tripalmitin, ceramides, bile acids, diacylglycerols, and other classes of metabolites) at Weeks 4, 13, 26, and 52.
- To determine the effect of TVB-2640 50 mg QD compared with matching placebo on glycosylated hemoglobin (HbA1c) levels among subjects with type 2 diabetes mellitus (T2DM) at Weeks 13, 26, 39, and 52.
- To determine the effect of TVB-2640 50 mg QD compared with matching placebo on Fibrosis 4 score (FIB-4) at Weeks 4, 13, 26, and 52.
- To use digital pathology to perform zonal analysis of fibrosis at Week 52.
 - To use digital pathology to evaluate the concurrence of fibrosis with components of the NAS score.
 - To use digital pathology to evaluate the NAS components.
- To correlate changes in MRI-PDFF with changes in, or baseline levels of, serum biomarkers and explore predictive markers of response.
- To explore the relationship between changes in, or Baseline levels of, serum biomarkers and histology results, and explore predictive markers of response.
- To explore the relationship between MRI-PDFF results and histology results.
- To correlate the presence of relevant single-nucleotide polymorphisms (SNPs) or other genes relevant to NAFLD or NASH with clinical and histopathologic response.
- To determine the effect of TVB-2640 50 mg QD compared with matching placebo on gut microbiome change from Baseline to Weeks 26 and 52 in a subset of subjects.
- To explore the relationship between nutrition, as measured by the HepVita Nutritional Survey, and clinical, histopathological, and biomarker changes in NASH at Weeks 26 and 52 in a subset of subjects.

In the event a subject is unable to complete the end of treatment MRI-PDFF and/or liver biopsy within the protocol-specified window (Week 52 +/- one week), extended dosing is permitted to maintain continuous dosing up to the time both assessments are completed, to a maximum total of 56 weeks of dosing. In this instance, the Follow-up visit at Week 56 for post treatment safety and efficacy assessments is to be adjusted to occur four weeks after the last dose (+/- one week).

In the instance of a dose hold due to an AE or SAE, the decision to resume study drug will require consultation with the Investigator, the CRO's Medical Monitor, and the Sponsor's Chief Medical Officer.

Improvement of NAS and improvement of fibrosis score will be evaluated by comparison of Baseline and Week 52 liver histology specimens. Subjects will also undergo MRI-PDFF prior to the start of treatment, at Week 26, and at Week 52 or Early Termination unless it presents a logistical or physical hardship to the subject. MRI-PDFF is not required at Early Termination if a subject has completed less than 22 weeks of study treatment. Other efficacy and pharmacodynamic (PD) assessments include FibroScan with CAP, and measurement of liver aminotransferases, lipid parameters, and other noninvasive biomarkers of NASH and liver fibrosis throughout the study.

During the study, safety will be assessed by vital signs, 12-lead electrocardiograms (ECGs), physical examinations including eye examinations, and clinical laboratory testing. Subjects will be evaluated for AEs and concomitant medication use throughout the study.

Blood samples will be collected at Baseline (Day 1) and at Weeks 4, 13, 26, and 52 for the assessment of sparse PK. In addition, blood samples will be collected on Day 1 and at Week 4 from a subset of subjects for serial PK.

An independent data monitoring committee (IDMC) will be established by charter to provide independent review and assessment of study data and to monitor the overall study conduct in a systematic manner to safeguard the safety of study subjects. The IDMC will be tasked with making recommendations to the Sponsor to continue, amend, or stop the study based on these assessments.

4.2. Randomization and Blinding

This will be a double-blind, randomized study. Subjects will be centrally assigned to randomized study treatment using an Interactive Web-based Response System (IWRS).

Approximately 162 unique subjects with liver fibrosis stage F2-F3 will be enrolled and randomized (2:1 ratio) to receive TVB-2640 50 mg or placebo (approximately 108 for TVB-2640 50 mg and approximately 54 subjects for placebo) PO QD for 52 weeks. Dynamic allocation is used for the randomization, stratified by T2DM status (Yes, No), region (North America, not North America), and amount of fibrosis (F2 or F3).

All subjects, Investigators, the Sponsor, and the clinical research organization (CRO) will be blinded to the treatment assignment of each individual subject. Members of the IDMC and the IDMC's independent statistician will be unblinded to treatment assignment as needed. In addition, specific vendors whose role in study conduct requires them to be unblinded (e.g., personnel operationally associated with the IWRS) may also be unblinded.

4.3. Sample Size Considerations

The study is powered to test the one-sided (statistical) superiority hypothesis stipulating that a TVB-2640 50-mg dose provides better benefit than placebo based on the primary efficacy endpoint. The study estimated total sample size is approximately 162 randomized subjects (108 on TVB-2640 and 54 on placebo). The sample size was derived using the normal approximation to the binomial distribution, and the estimated power to detect a difference in the primary efficacy response of 20% (TVB-2640 40% and placebo 20% at Week 52) was at least 80% (one-sided test at the 0.05 significance level). A 2-to-1 randomization allocation was assumed (TVB-2640 to placebo), and an anticipated dropout rate of 18.5% was also applied to estimate the final total sample size (N=162).

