- Interim Analysis Modified Intention-to-Treat (IAmITT): Comprises a subset of subjects in the ITT population with 8% \geq MRI-PDFF at screening or at baseline with at least 1 evaluable post-Baseline MRI-PDFF value, defined as an MRI-PDFF assessment obtained at least 22 weeks after the first dose of study drug.
- The Safety analysis set: Comprises all subjects who are randomized and received at least 1 dose (partial or complete) of study drug.
- PK Population: Comprises all subjects in the ITT population with available PK measurements.

Power considerations and sample size determination: The study estimated total sample size is approximately 162 randomized subjects (108 on TVB-2640 and 54 on placebo). The sample size was derived using the normal approximation to the binomial distribution, and the estimated power to detect a difference in the primary efficacy response of 20% (TVB-2640 40% and placebo 20% at Week 52) was at least 80% (one-sided test at the 0.05 significance level). A 2-to-1 randomization allocation was assumed (TVB-2640 to placebo). An anticipated dropout rate of 18.5% was also applied to estimate the final sample size (N=162).

Safety Analyses

Safety data will be evaluated for the Safety population on the basis of treatment-emergent adverse events (TEAEs), clinical laboratory assessments, vital signs, ECGs, weight, and physical examinations. Changes from Baseline in key clinical laboratory measurements, vital signs, physical examinations, and weight will be summarized by treatment group using standard descriptive statistics. TEAE incidence rates will be summarized using frequency and percentage for each treatment group and in total. TEAEs through 30 days after the last dose of study treatment will be summarized by MedDRA

[figure not shown]
(current version) system organ class, and preferred term. AEs will also be summarized by National Cancer Institute Common Terminology Criteria for Adverse Events (NCI CTCAE) (current version) grade, and by causality (attribution to study treatment, related/not related to investigational medicinal product). All safety data will be presented in data listings.

Interim Analysis

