13.5. Power Considerations and Sample Size Determination

The study is powered to test the one-sided (statistical) superiority hypothesis stipulating that a TVB-2640 50-mg dose provides better benefit than placebo based on the primary efficacy endpoint. The study estimated total sample size is approximately 162 randomized subjects (108 on TVB-2640 and 54 on placebo). The sample size was derived using the normal approximation to the binomial distribution, and the estimated power to detect a difference in the primary efficacy response of 20% (TVB-2640 40% and placebo 20% at Week 52) was at least 80% (one-sided test at the 0.05 significance level). A 2-to-1 randomization allocation was assumed (TVB-2640 to placebo), and an anticipated dropout rate of 18.5% was also applied to estimate the final total sample size (N=162).

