6. ANALYSIS POPULATIONS/SETS

Intention-to-Treat (ITT) Population: The principal analysis of the primary and secondary efficacy endpoints will be based on the Intention-to-Treat (ITT) population, which comprises all randomized subjects; this population will serve as the basis for all efficacy analyses. Subjects' data will be analyzed according to their randomized treatment assignment.

Modified Intention-to-Treat (mITT) Population: Comprises all subjects in the ITT population who have completed at least 42 weeks of treatment and have an evaluable post treatment histological assessment. Subjects will be analyzed according to the randomized treatment assignment.

Interim Analyses Modified Intention-to-treat (IAmITT) Population: Comprises a subset of approximately 60 subjects in the ITT population with 8% \geq MRI-PDFF at screening or at baseline with at least 1 evaluable post-Baseline MRI-PDFF value, defined as an MRI-PDFF assessment obtained at least 22 weeks after the first dose of study drug.

Safety (SAF) Population: Consists of all randomized subjects who received at least 1 dose (partial or complete) of study drug. This population will be used for all summaries of subject accountability, demographic and baseline data, and safety information, including AE incidence, clinical laboratory data, ECG data, and vital signs data. Subjects' data will be summarized according to the treatment they received. If all subjects were dosed according to randomized treatment assignment, then the safety and ITT analysis sets are identical.

PK Population: Comprises all ITT subjects with available PK measurements.

Serial PK Population: Comprises the subset of subjects who provided blood samples for evaluation of serial PK at timepoints on Day 1 and at Week 4.

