9. EFFICACY

9.1. Primary Efficacy Endpoint Analyses

9.1.1. Principal Analysis of the Primary Efficacy Endpoints

The principal efficacy analyses will be conducted on the ITT population. Additional sensitivity and supplementary analyses will be performed for the primary efficacy endpoints, as described in the next section.

The treatment groups will be compared based on the primary efficacy endpoints using one-sided Cochran-Mantel-Haenszel (CMH) tests stratified by the randomization stratifications T2DM status at baseline (yes or no) and amount of fibrosis at baseline (F2 or F3).

Mathematically, the null and alternative hypotheses for the primary efficacy endpoints are stated as:

$$H_0: p_T \leq p_p$$

$$H_a: p_T > p_p$$

Where, p_T is the proportion of responders in the TVB-2640 50-mg treatment group and p_p is the proportion of responders in the placebo treatment group. The higher responder proportion is a better outcome.

A Clopper-Pearson 90% and 95% CI will be derived for each treatment group, and the stratified CMH odds ratio (with its 90% and 95% CI, using the control group as a reference group) will be produced to assess the treatment effect magnitude. The difference in treatment groups response rates will be provided and also be characterized by the 90% and 95% CIs using Miettinen and Nurminen (1985).

Subgroup analyses of the primary efficacy endpoints will be performed to assess whether the treatment effect is concordant among subgroups. The planned subgroup analyses are described in Section 7.2. Analyses will be performed if there is an adequate number of subjects in each subgroup.

A subject who discontinues treatment prior to Week 42, does not provide a histological assessment on or after Week 42, or who otherwise has missing data will be considered a non-responder.

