9.1.2. Sensitivity Analyses of the Primary Efficacy Endpoints

Evaluation of the robustness of the principal analysis of the primary efficacy endpoints will be carried out using the following (4) four approaches:

- A logistic regression with response as a dependent variable; treatment group, randomization stratification factors (T2DM status at baseline [yes or no] and amount of fibrosis at baseline [F2 or F3]) as independent factors; and age as a baseline covariate.
- The analysis of the primary efficacy endpoints will be repeated for the modified Intention-to-Treat (mITT) population to ascertain any changes in the conclusion of the principal analysis findings.
- A repeat of the primary efficacy analysis principal analysis (CMH test) for the following three ITT subsets:
 - ITT Subjects who achieve at least 50% of total cumulative study drug dose (i.e., at least **9100 mg** 52-week total dose (based on a total of 50 mg.kg x 52 weeks x 7 days = 18200 mg x weeks x days).
 - ITT Subjects who achieve at least 70% of total cumulative study drug dose (i.e., at least **12740 mg** 52-week total dose (based on a total of 50 mg x 52 weeks x 7 days = 18200 mg x weeks x days).
 - ITT Subjects who achieve at least 80% of total cumulative study drug dose (i.e., at least **14560 mg** 52-week total dose (based on a total of 50 mg.kg x 52 weeks x 7 days = 18200 mg x weeks x days).
- To assess the impact of missing data in the primary endpoint analyses, multiple imputation procedure will be carried out using MAR assumption with Fully Conditional Specification method for binary endpoint in SAS PROC MI. 100 imputations will be performed. The CMH test statistic from each imputed dataset will be based on Wilson-Hilferty transformation (Wilson & Hilferty, 1931) and will be combined using PROC MIANALYZE. Combined CMH test statistic and p-value will be computed. The method described in Ratitch, Lipkovich, and O'Kelly (2013) will be used to combine the results.

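### The stated power of at least 80% fits 132 completers; for the planned ITT analysis it is about 73% to 78% if 40%/20% are completer rates, and the documents do not say whether they are

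*SAP*

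**What the plan says.** **Design calculation.** The protocol synopsis, Protocol 13.5 and SAP 4.3 carry the same calculation: 40% against 20%, 2:1 allocation, one-sided 0.05, 108 and 54 randomized. SAP 4.3 gives the rates and the power as "TVB-2640 40% and placebo 20% at Week 52) was at least 80% (one-sided test at the 0.05 significance level". On method, Protocol 13.5 says only that "The sample size was derived using the normal approximation to the binomial distribution". On dropout, SAP 4.3 says that "an anticipated dropout rate of 18.5% was also applied to estimate the final total sample size (N=162". No section says whether the two rates refer to subjects with an evaluable Week 52 biopsy or to everyone randomized, or which variance form was used.

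**Principal analysis.** SAP 6 bases it on the ITT population, "which comprises all randomized subjects; this population will serve as the basis for all efficacy analyses". SAP 9.1.1 prescribes a one-sided stratified CMH test. A subject who stops before Week 42, has no histology from Week 42 on, "or who otherwise has missing data will be considered a non-responder". Protocol 13.2.1 has the same rule, but also a sentence restricting eligibility for the primary endpoint analysis to subjects with at least 42 weeks of treatment and a posttreatment biopsy.

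**Endpoint.** SAP 4.3 says the trial is powered to show that a "TVB-2640 50-mg dose provides better benefit than placebo based on the primary efficacy endpoint", in the singular. SAP 5.1 and 7.4 define two co-primaries, 1A and 1B, and SAP 11 records that they were added.

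**The concern.** Dividing by one minus the dropout rate is the right inflation when dropouts leave the analysis: enough completers remain, and they respond at the design rates. Here dropouts stay in the denominator and count as failures. The inflation then restores the number of subjects but not the effect, because both rates and their difference shrink. A power figure worked out for completers does not carry over to an ITT analysis with non-responder imputation.

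At stake is a headline design figure. If 40% and 20% are completer rates, the chance of missing the design effect in the principal analysis is above the 20% that the documents imply as its upper limit. Type I error, the test and the estimates are not affected.

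**Working it through.** **Inputs** (SAP 4.3, Protocol 13.5): p_T = 0.40, p_P = 0.20, one-sided 0.05, 80% power, 2:1, dropout 0.185, 108/54 randomized.

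**Step 1: reproduce N.** Unpooled normal approximation:

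n_P = (1.645 + 0.842)² × (0.20×0.80 + 0.40×0.60/2) / 0.20² = 6.183 × 0.28 / 0.04 = 43.28, rounded up to 44.

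Total 44 + 88 = 132, and 132/0.815 = 161.96, i.e. 162. Power at 88/44 is Φ(0.20/√(0.24/88 + 0.16/44) − 1.645) = Φ(2.507 − 1.645) = 80.6%.

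Of eight formula variants tried, only this one returns 162. With null variance for the critical value, N is 147, or 180.4 after dropout; arcsine gives 144, or 176.7; pooled variance throughout gives 156, or 191.4; the four continuity-corrected variants give 187.7 to 217.2. Multiplying by 1.185 instead of dividing by 0.815 never gives 162 (unpooled: 156.4).

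**Step 2: completer reading, all dropouts counted as failures, equal by arm.** The rates become 0.40 × 0.815 = 0.326 and 0.20 × 0.815 = 0.163, a difference of 0.163. At 108/54:

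- SE1 = √(0.326×0.674/108 + 0.163×0.837/54) = 0.0675
- pooled rate (108×0.326 + 54×0.163)/162 = 0.2717, so SE0 = √(0.2717×0.7283×(1/108 + 1/54)) = 0.0741
- unpooled: Φ(0.163/0.0675 − 1.645) = 77.9%
- null variance, as in the CMH: Φ((0.163 − 1.645×0.0741)/0.0675) = 72.8%

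Exact enumeration of the unstratified CMH gives 73.5%. Stratified CMH simulation with non-prognostic strata gives about 72% to 74% for the SAP's four cells or the protocol's eight (which include region). Assumed prognostic strata raise this to about 77%.

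**Step 3: ITT reading.** With 0.40 and 0.20 at 108/54, SE1 = 0.0720 and SE0 = 0.0786. Power is 83.7% with null variance, 84.0% by exact CMH and 87.1% unpooled.

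**Step 4: where the gap in Step 2 comes from.**

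| | 88/44, 40% vs 20% | 108/54, 32.6% vs 16.3% |
|---|---|---|
| Unpooled | 80.6% | 77.9% |
| Null variance | 76.2% | 72.8% |

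The variance form accounts for 4.4 to 5.1 points, and counting dropouts as failures for 2.7 to 3.4.

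**Step 5: sensitivity, completer reading.** The share of the 18.5% that ends as non-response is an assumption. Not every dropout need lack histology: footnote e of the schedule of assessments still requires a biopsy from early terminators with at least 42 weeks of treatment.

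| Share imputed | Null variance | Unpooled |
|---|---|---|
| All | 72.8% | 77.9% |
| Three-quarters | 75.8% | 80.5% |
| Half | 78.7% | 82.9% |

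Power falls below 80% once 6.9% of each arm (null variance) or 14.8% (unpooled) become non-responders through dropout. With 18.5% overall but unequal arms, null-variance power is 66% (placebo 15%, active 20.2%) to 79% (placebo 22%, active 16.7%).

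**The case against.** The strongest reply is that no printed figure is shown to be wrong. The documents attribute the power to a normal approximation, not to the CMH test, and by that method 40% against 20% does give 80.6% at 88/44. Planning with a simple approximation and analysing with a stratified test is ordinary practice. The rates may already be ITT rates. The inflation does not settle the reading, because it also serves the mITT repeat: SAP 9.1.2 says the primary analysis "will be repeated for the modified Intention-to-Treat (mITT) population to ascertain any changes in the conclusion of the principal analysis findings".

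Much of this stands. The completer reading is inferred, and more of the gap comes from the variance form than from the treatment of dropouts. In the plan's own formula the shortfall below 80% is about 2 points with all dropouts imputed, and it vanishes when three-quarters or fewer are. The timing also limits the consequence: the SAP rests on a protocol dated 06 September 2023, and the synopsis expected the last subject to complete that month, so restating power alters no enrolment decision.

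It does not dispose of the point. The two readings fall on opposite sides of 80%, and nothing in the documents chooses between them. If the rates were ITT rates, the principal analysis would need no inflation. The completer sentence in Protocol 13.2.1 points the same way as the arithmetic. The mITT argument does not rescue the figure under the completer reading either, since 88/44 with null variance gives 76.2%.

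A reader might go further and infer that N=162 is a miscalculation, or that the trial is underpowered at 73% as a matter of fact. The documents support neither: N reproduces exactly, and 73% depends on an unstated population and on assumed dropout behaviour.

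**Conclusion.** The point holds conditionally. On the better-supported reading, the stated minimum of 80% belongs to 132 completers under the unpooled approximation. The principal ITT analysis then has about 73% power with CMH-type variance, or 78% by the plan's own formula. This rests on all 18.5% becoming non-responders, equal dropout by arm and, for the CMH figure, non-prognostic strata. On the ITT reading, power is about 84% and the statement is true.

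It should be corrected because the figure cannot be verified for the analysis that it is taken to describe. Confidence is medium, because the reading is inferred.

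Separately, SAP 4.3 cannot be read as giving power for 1A or 1B. A reader might infer that 1B is poorly powered, but the documents give no response rates for it, so neither adequate nor inadequate power can be derived.

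**What to change.** No added subjects and no change to the test.

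1. In the protocol synopsis, Protocol 13.5 and SAP 4.3, state which population 40% and 20% describe and which variance form was used. Show the step from 132 to 162.
2. If they are completer rates, say that 80% applies to 132 completers by the unpooled approximation. Restate ITT power as about 73% (CMH-type variance) to 78% (unpooled), with all 18.5% counted as non-responders and with equal dropout and non-prognostic strata assumed.
3. If they are ITT rates, say so and state about 84%.
4. Reconcile the sentence in Protocol 13.2.1 that limits the primary analysis to subjects with at least 42 weeks of treatment and a biopsy with the ITT rule in the same section.
5. In SAP 4.3, add that the calculation was made for the protocol's single either/or endpoint and gives no power for co-primaries 1A and 1B.

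The cost is wording in three places plus one sentence in Protocol 13.2.1. Under the completer reading, the published power becomes less favourable.
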